### **2.3.4. In-hospital activity**

Registration of activity level during hospitalisation will be performed by means of pedometers in those centers that have access to these devices. Both amount of steps and step length will be noted, and total walked distance per day can hereby be calculated.

### **2.3.5. Nutritional status**

Nutritional state of the patient will be registered through the Mini-Nutritional Assessment – Short Form (MNA-SF) [25]. For diagnosis of malnutrition, the new Global Leadership Initiative on Malnutrition (GLIM)-criteria will be used [26].

### **2.3.6. Questionnaires**

The SARC-F [27] and FRAIL-scale [28] will be completed as routine screening questionnaires for sarcopenia and frailty, respectively. The SAR-QOL questionnaire will be used to evaluate the self-reported quality of life [29].

## **2.4. Statistical analysis**

Databases will be kept up in a Microsoft Access database.

Statistical analysis will be done by using SPSS Statistics version 24. Descriptive analyses will be used for determining the clinical and demographic characteristics. A Kolmogorov-Smirnov test will be used to verify the normal distribution of the different variables. Further statistical analyses will be performed by Chi Square test, Fisher exact, Mann-Whitney U test or Fisher exact test, depending on the distribution and the nature of the variables analysed. P-values of  $\leq 0.05$  will be considered statistically significant.

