## Abstract

Sarcopenia is a geriatric syndrome defined as progressive and generalized age-related muscle loss with decline in muscle mass and muscle function (either strength or performance). It is closely related to adverse outcomes such as frailty, reduced quality of life, increased risk of falling, more frequent hospitalisations and higher mortality. Acute sarcopenia is the decline of muscle mass and function following acute disease or hospitalisation, sufficiently to meet the criteria of sarcopenia.

Objectives: To assess the effect of hospitalisation and acute illness on muscle mass and function, and to assess which other factors contribute to the development of acute sarcopenia.

Study design and main outcome measures: This study is a prospective multicenter observational study. Patients admitted to acute geriatric wards of different European centers and hospitalised for at least 5 days will be included. Measurements of muscle mass will be performed via ultrasound. Measurements of muscle function will be done by hand grip strength using Jamar dynamometer and by gait speed using the 4-meter walking test, when feasible. Other parameters will be measured via file study, laboratory investigations or validated questionnaires. Activity levels during hospitalisation will be measured through pedometers.

Anticipated results: Decline of muscle mass and muscle characteristics secondary to hospitalisation. We also expect an association with reasons of hospitalisation, pre-existing conditions, laboratory results and nutritional status prior to hospitalisation on the decline in muscle parameters.

Conclusions: This study seeks to gain knowledge of the development of acute sarcopenia and its contributing factors.

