### 1.1. Objective

The aim of this study is to investigate the effect of hospitalisation due to acute illness on muscle mass characteristics, assessed in older adults through ultrasound. The primary endpoint is the change of characteristics of muscle mass in function of time since admission. The secondary endpoint of the study is to identify health related parameters associated with the development of acute sarcopenia. Relevant determinants of the evolution of muscle

mass and muscle strength since admission (reason of hospitalisation, comorbidities and laboratory data) will therefore also be investigated.

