## **1.2. Hypothesis**

Hospitalisation and acute illnesses will negatively affect both muscle mass and muscle function and will hereby contribute to the development of acute sarcopenia. We hypothesize that hospitalisation due to an elevated degree of inflammation will lead to more severe decrease of muscle mass and muscle function than hospitalisation due to non-inflammatory reasons. Furthermore, certain pre-existing conditions are supposed to increase the risk of acute sarcopenia.

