### 2.3.2. Muscle mass

In order to obtain reliable and consistent measurements, all ultrasonography will be done by an ultrasonographist that is trained to perform the measurements proposed. For the measurements, a linear probe of 5 cm width will be used. Frequency of the beam will be set on 12 MHz.

Patients should not have had any physical exercise in the 30 minutes before the measurement. Muscles should be completely relaxed and patients should be placed in the supine position, with hips in neutral position and knees fully extended. The dominant leg will be taken for the measurements. To calculate the relative muscle thickness values, the total length of muscle will be noted.

Ultrasonographic data of the four bellies of the quadriceps muscle (rectus femoris, vastus lateralis, vastus medialis, vastus intermedius) will be taken. Measuring points will be specified according to the propositions of the SARCUS-working group [19]. Muscle thickness, fascicle length, pennation angle, muscle cross-sectional area and echo-intensity of all muscles listed will be taken.

The first measurement will be taken as early as possible within 48 hours after admission at the latest. Follow-up measurements will be taken according to the type of ward the patient is admitted to. For patients that are expected to be hospitalized for a limited time (<5 days), the follow-up measurement will be done 3 days after initial measurement. For patients that are expected to be hospitalized for a longer time (>7 days), measurements will be repeated 7

days after initial measurement, to be repeated after another 7 days as long as the patient is hospitalized.

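### Section 2.4 gives the primary endpoint, within-patient muscle change over time, no paired or longitudinal method and no estimate of change

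*Combined protocol and SAP*

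**What the plan says.** Section 1.1 (Objective): "The primary endpoint is the change of characteristics of muscle mass in function of time since admission".

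Section 2.3.2 (Muscle mass) obtains that change by scanning each patient more than once.
- Baseline: "The first measurement will be taken as early as possible within 48 hours after admission at the latest".
- Short expected stays: when a patient is expected to be "hospitalized for a limited time (<5 days), the follow-up measurement will be done 3 days after initial measurement".
- Longer expected stays: "For patients that are expected to be hospitalized for a longer time (>7 days), measurements will be repeated 7" days after the first scan, and weekly after that for as long as the patient stays.

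The data for the primary endpoint are therefore repeated measurements, unequal in number and spacing between patients.

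Section 2.4 (Statistical analysis) is the only text on analysis. For description: "Descriptive analyses will be used for determining the clinical and demographic characteristics". For inference: "Further statistical analyses will be performed by Chi Square test, Fisher exact, Mann-Whitney U test or Fisher exact test". The choice among these depends on the distribution and type of variable. A Kolmogorov-Smirnov check of normality is planned, and the significance level is 0.05. No test is tied to any endpoint.

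Section 1.2 adds a question about differences between patients: "We hypothesize that hospitalisation due to an elevated degree of inflammation will lead to more severe decrease of muscle mass and muscle function", compared with admissions for non-inflammatory reasons.

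**The concern.** The main question is whether muscle declines during the stay and by how much. That calls for a method that uses each patient as their own control and reports a size of change. The inferential list in section 2.4 contains neither, and the descriptive sentence covers clinical and demographic characteristics, not muscle change.

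The list also does not show what was intended. Fisher exact appears twice, and a normality check is planned although no parametric test is named for normal data.

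At stake is the primary result. An analyst must either choose a method after the data are in or make do with the list. Section 2.3.2 collects five ultrasound parameters on four muscle bellies, 5 x 4 = 20 variables, and none is named as primary. A method chosen late therefore leaves wide room for selection.

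**Working it through.** **Step 1. What each listed test can answer.**
- Mann-Whitney U on one change score per patient compares two groups of patients. It suits the inflammation hypothesis in section 1.2. It does not show whether muscle changed overall.
- Chi-square and Fisher exact compare proportions between groups.
- A one-sample chi-square on decliners versus gainers would test the direction of change. The plan does not state this use, and it gives no size. The share of decliners is Phi(d / sqrt(2(1 - r))), where d is the decline in SDs of a single scan and r the correlation between two scans. For (d, r) = (0.1, 0.9), (0.2, 0.6) and (0.3, 0.1) the argument is 0.1/0.447 = 0.2/0.894 = 0.3/1.342 = 0.224, so the share is 58.8% each time. Declines that differ threefold look the same.

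None of these uses estimates the primary endpoint.

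**Step 2. Illustration of ignoring the pairing.** The plan has no figure to reproduce: it gives no n, SD, effect size or correlation. Assumed inputs: n = 100 patients scanned twice, d = 0.2, r = 0.5, 0.8 or 0.9, two-sided 0.05, normal data.

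The mean change has true standard error sqrt(2(1 - r)/n) = 0.100, 0.0632 or 0.0447. An analysis that treats the two visits as separate samples uses sqrt(2/n) = 0.141, so it needs an observed change of 1.96 x 0.141 = 0.277.

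- Unpaired power, about Phi((0.2 - 0.277)/SE): Phi(-0.77) = 22%, Phi(-1.22) = 11%, Phi(-1.73) = 4%.
- Paired power, about Phi(0.2/SE - 1.96): Phi(0.04) = 52%, Phi(1.202) = 89%, Phi(2.51) = 99%.
- Unpaired rejection with no change at r = 0.5: 0.277/0.100 = 2.77, which is 0.6% two-sided. It is close to zero at the higher correlations.

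Simulation of the actual rank tests agrees. Mann-Whitney across visits has power of about 21%, 11% and 5-7%. Signed-rank has 49%, 87% and 99%. With no change, Mann-Whitney rejects in 0-1.0% of runs and signed-rank in 4.4-5.2%.

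**Step 3. How the loss depends on the assumptions** (simulated power, r = 0.5/0.8/0.9):

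| Decline | n | Mann-Whitney across visits | Signed-rank |
|---|---|---|---|
| 0.1 SD | 400 | 21/11/4% | 48/87/99% |
| 0.2 SD | 200 | 50/49/50% | 79/99/100% |
| 0.2 SD | 400 | 86/96/99% | 97/100/100% |
| 0.3 SD | 200 | 91% or more | 98% or more |

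**Step 4. Precision of an estimate.** At n = 100 a paired 95% CI has half-width 1.96 x sqrt(2(1 - r)/n) = 0.196, 0.124 or 0.088 SD. Treating the visits as unpaired gives 0.277 SD.

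**The case against.** The listed tests are not wrong in themselves. Mann-Whitney on change scores between groups, and Chi-square or Fisher exact on group proportions, are sound for the hypothesis in section 1.2 and for the secondary aim. That stands, and the fix keeps them. The direction test in Step 1 is also usable: with no true change it rejected in 4.9-6.7% of runs against a nominal 5%. It still gives no size of decline.

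The power figures price a use that the plan never states. That stands too. A reader might infer that the authors mean to run Mann-Whitney on admission versus follow-up scans. Section 2.4 ties no test to any endpoint, so the documents do not support that inference. Nor do they support a fear of spurious declines, because ignoring the pairing here is conservative. Nor is the loss of power general: at 0.2 SD and 400 patients it is small. The Discussion calls the size of the study a strength, but gives no number with which to judge this.

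It may be said that any analyst would turn to a paired method unprompted. That may be so, but the method, variable and interval would then be chosen with the data in hand.

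**Conclusion.** The point holds as an omission in the text. The primary endpoint is change within patients over time, and section 2.4 offers only tests suited to independent groups. It plans no paired or longitudinal method and no estimate of change with a confidence interval, and no other section supplies one. This must be fixed, because the main question has no stated analysis.

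That conclusion rests on the wording alone. The size of the power loss does not follow from the documents. It is an illustration that depends on the assumed n, effect, correlation and normality, and on a use of Mann-Whitney that the plan does not describe.

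**What to change.** In section 2.4, add:

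> Primary endpoint: for the ultrasound variable that the sponsor names as primary before analysis, all scans are analysed in a linear mixed model with actual days since the first scan as time, a random patient effect, a centre effect, and the follow-up schedule assigned at baseline as a factor. The estimated change at one interval named in advance is the single primary result, reported with a 95% CI. As a supporting analysis, each patient's change from the first scan to the first follow-up scan is tested with the Wilcoxon signed-rank test and reported with a 95% CI, by follow-up interval, with the number of patients who have no follow-up scan.

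The model should lead because the endpoint is defined as a function of time and long-stay patients are scanned weekly. A comparison of the first two scans alone would drop the later ones.

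Also:
- Record the date of each scan. Section 2.3.1 lists admission and discharge dates but does not mention scan dates.
- Keep Mann-Whitney (on one change score per patient), Chi-square and Fisher exact for between-group comparisons, and delete the duplicate Fisher entry.

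Cost: a sponsor decision on the primary variable and interval, and a little more analysis. The model assumes that discharge depends only on observed data, which should be stated. The supporting analysis describes only patients with a follow-up scan. No more patients or scans are needed.

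A separate point for the sponsor: the Abstract says "Patients admitted to acute geriatric wards of different European centers and hospitalised for at least 5 days will be included", while section 2.3.2 has schedules for expected stays under 5 and over 7 days. These passages must be reconciled.

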## 2.3. Measurements

### 2.3.1. Patient characteristics

Date of birth, gender, height and weight will be registered. If the patient is bedridden, weight can be measured through either weight chairs or weight measuring lifts. Height will be estimated using the ulna length or knee height [20]. Date of admission and discharge will be noted. The home care setting of the patient will be registered. The main reason of hospital admission will be registered.

Comorbidities on admission will be registered through the Cumulative Illness Rating Scale for Geriatrics (CIRS-G) [21]. The CIRS-G was designed to estimate the survival of elderly persons, assessing disease severity using a score from 0 to 4 in 14 different categories of organ systems: cardiac, vascular, hematological, respiratory, ophthalmological and otorhinolaryngological, upper gastro-intestinal, lower gastro-intestinal, hepatic and pancreatic, renal, genito-urinary, musculoskeletal and tegumental, neurological, endocrine/metabolic/breast and psychiatric [22]. Score '0' stands for 'no problem affecting that system', score '1' stands for 'current mild problem or past significant problem', score '2' stands for 'moderate disability or morbidity', score '3' stands for 'severe problem' and score '4' stands for 'extremely severe problem'.

Laboratory values that will be checked are either nutritional through albumin and prealbumin, inflammatory through C-reactive protein (CRP) and white blood cell count, and the measurement of 25-hydroxyvitamin D (25-OH-vitamin D). Blood samples will be collected on day of admission. Laboratory values that are not expected to fluctuate strongly (albumin, pre-albumin, 25-OH-vitamin D) will be taken within the first 5 days of admission.

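### The tests named in section 2.4 cannot relate a numeric determinant to a numeric change in muscle, and the inflammatory group is left undefined

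*Combined protocol and SAP*

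**What the plan says.** Section 2.4 gives the whole analysis plan in one paragraph. After descriptive statistics comes a check of distribution: "A Kolmogorov-Smirnov test will be used to verify the normal distribution of the different variables". The inferential methods follow: "Further statistical analyses will be performed by Chi Square test, Fisher exact, Mann-Whitney U test or Fisher exact test, depending on the distribution". That is three distinct tests, since Fisher exact appears twice. The significance level is 0.05, with sidedness not stated.

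Section 1.1 sets the outcome: "The primary endpoint is the change of characteristics of muscle mass in function of time since admission". Section 2.3.2 shows that it is measured on numeric scales: "Muscle thickness, fascicle length, pennation angle, muscle cross-sectional area and echo-intensity of all muscles listed will be taken". Grip strength and gait speed (section 2.3.3) are numeric too. The sentence in section 1.1 on determinants ends: "mass and muscle strength since admission (reason of hospitalisation, comorbidities and laboratory data) will therefore also be investigated".

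Many of those determinants are also numbers. Section 2.3.1 lists albumin, prealbumin and 25-OH-vitamin D, and adds markers that are "inflammatory through C-reactive protein (CRP) and white blood cell count". A CIRS-G total, the MNA-SF score (section 2.3.5) and pedometer steps, in centers that have the devices (section 2.3.4), are of the same kind.

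Section 1.2 predicts that "hospitalisation due to an elevated degree of inflammation will lead to more severe decrease of muscle mass and muscle function" compared with admission for causes that are not inflammatory. No section gives a CRP or white-cell limit, or a list of admission reasons that belong to the inflammatory group.

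**The concern.** Chi-square and Fisher exact need both variables in categories. Mann-Whitney U needs one variable that forms exactly two groups. To relate CRP to a change in rectus femoris thickness with these tests, the analyst has to cut CRP, cut the thickness change, or cut both. Cutting discards information that was collected, so the determinant analysis loses power without any gain.

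The cut also has to be placed somewhere, and the plan does not say where. Any threshold for the laboratory values would be picked at the analysis stage. For inflammation this touches a stated hypothesis, because membership of the inflammatory group is open whether it is set by admission reason or by a marker.

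A smaller point is that Mann-Whitney handles two groups only, while the main reason for admission can have more than two levels. None of this depends on adjustment for confounders or on a within-patient method. It would hold for one determinant taken alone.

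**Working it through.** **Inputs.** The documents supply the tests, the 0.05 level, and the measures listed above. They give no sample size, effect size or power, so there is no figure of the plan to reproduce. Two-sided testing, the shape of the determinant and the correlation ρ are assumptions here.

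**Step 1: what each test accepts.** Chi-square and Fisher take category against category. Mann-Whitney takes a number against two groups. Kolmogorov-Smirnov is used only to check normality. Nothing takes number against number.

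**Step 2: information kept after one cut.** For a normal determinant with a linear effect, cut so that a share p lies on one side, the information kept relative to linear regression is E = φ(z_p)² / [p(1−p)]. At the median this is 0.3989² / 0.25 = 0.637, that is 2/π. If Mann-Whitney is then used, multiply by 3/π. If the comparison is with Spearman rather than regression, divide that by 9/π².

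| Cut | Split vs regression | Split + Mann-Whitney vs regression | Split + Mann-Whitney vs Spearman |
|---|---|---|---|
| 50/50 | 0.637 | 0.608 | 0.667 |
| 25/75 | 0.539 | 0.514 | 0.564 |
| 20/80 | 0.490 | 0.468 | 0.513 |
| 10/90 | 0.342 | 0.327 | 0.358 |

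The loss is therefore 33 to 39% at the median and 49 to 53% at 20/80. Cutting both sides at the median keeps 0.637² = 0.405, a loss of 60%.

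**Step 3: other shapes (1,000,000 draws each).** A uniform or clearly two-peaked determinant cut at its median keeps about 0.75. With Mann-Whitney that is 0.75 × 3/π = 0.716. The loss is then 25 to 28%. With a linear effect on the raw scale and cuts from the 50th to the 90th percentile, an exponential determinant loses 35 to 52% and a lognormal one (log-SD 1) 46 to 73%, before the Mann-Whitney factor. If the true effect is a step exactly at the cut, grouping loses nothing.

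**Step 4: what this means in patients (assumed ρ, 80% power, two-sided 0.05).** For regression, n = [(1.960 + 0.842)/atanh(ρ)]² + 3.

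| | ρ = 0.2 | ρ = 0.3 |
|---|---|---|
| Regression or Pearson | 194 | 85 |
| Spearman | 213 | 93 |
| Median split, Mann-Whitney | 318 to 321 | 138 to 142 |
| Both sides split at the median | 476 | 207 |

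Simulated power (3,000 runs) at N = 194 and ρ = 0.2 was 81% for Pearson, 75% for Spearman, 58% for Mann-Whitney after a median split, and 40% for chi-square with both sides split. Cutting only the outcome, with 20% of patients on one side, and comparing the uncut determinant by Mann-Whitney gave 47%.

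**Step 5: a cut-point chosen from the data.** With no true association and a nominal 0.05 (5,000 runs each, N = 100, 200 and 400), keeping the best of three quartile cuts gave about 12% false positives. Searching nine deciles gave 24 to 25%, and searching every cut between the 10th and 90th percentiles about 41 to 44%.

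**The case against.** The best defence starts with section 1.2. Read in full, it compares admission for inflammation with admission for other causes. Section 2.3.1 registers the main reason for admission, and Mann-Whitney fits a comparison of two such groups without any cut of CRP. This stands. A reader might infer that the inflammation hypothesis can only be tested by cutting CRP, and the text does not support that. What remains open is which reasons count as inflammatory, or which marker level does if the wording is read as a threshold.

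Second, the secondary endpoint asks which parameters go with developing acute sarcopenia, which the Abstract defines as decline that meets the criteria for sarcopenia. That is a yes/no outcome, and Mann-Whitney can compare uncut CRP or albumin between the two groups. This also stands, although no ultrasound cut-off is given for that outcome. It does not cover the separate plan in section 1.1 to study determinants of the course of muscle mass and strength.

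Third, admission reason, single CIRS-G items and the GLIM diagnosis are categories already and need no split. That is correct, and the point is limited to the numeric determinants.

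Fourth, section 2.4 lets the choice depend on the distribution and type of the variables. That selects among the listed tests and adds none. The repeated Fisher entry may mean that a test dropped out in drafting, but nothing shows which.

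Fifth, regression of several determinants on 20 ultrasound measures (five on each of four muscle bellies) raises multiplicity. It does, and so would the same number of split comparisons. The change proposed here does not settle multiplicity.

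**Conclusion.** The point holds for numeric determinants of a numeric change in muscle mass or strength. Section 1.1 plans that analysis, and no method named in section 2.4 can do it without a split.

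For a roughly normal determinant with a linear effect, the avoidable loss is about a third to two fifths at a median split and about half at 20/80. It is not always a third or more: a uniform or two-peaked determinant cut at its median loses about a quarter, and a true step at the cut costs nothing. Patient numbers and power rest on assumed correlations and sample sizes.

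A reader might infer that the plan carries a false-positive rate of 12% or of 40% and more. The documents do not support that. No section announces a search over cut-points, and those rates arise only if the grouping is chosen from the data. The plan does leave that possibility open. Nor is inflammation the only directional hypothesis, since section 1.2 also predicts overall decline and higher risk with certain pre-existing conditions.

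This should be corrected. It weakens the determinant analysis and leaves one stated contrast undefined, but it does not invalidate the study.

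**What to change.** In section 2.4:

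- State that numeric determinants (CRP, white cells, albumin, prealbumin, 25-OH-vitamin D, CIRS-G total, MNA-SF score, and steps where recorded) are kept continuous, with CRP and white cells on the log scale.
- Relate them to change in muscle and strength by a regression that accounts for the differing follow-up times in sections 2.3.2 and 2.3.3 (3 days, or 7 days and then weekly). Report slopes with 95% confidence intervals, and Spearman correlation as a distribution-free check.
- Use Kruskal-Wallis, or a multi-level factor in the regression, for admission reason.
- Keep the two-group contrast of section 1.2, and write down before the data are seen which admission reasons, or which marker level, define the inflammatory group. Add log CRP as a supporting continuous analysis.
- Correct the repeated Fisher entry.

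The cost is wording only, with the same data and the same software. Section 3 says that no data were available at the time of writing, so on that statement the choices can be fixed without sight of results. The small downside is that slopes are less familiar to readers than two-group comparisons.

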## **2. Methods**

### **2.1. Study design**

A prospective, multicenter, international observational study will be conducted. The study is designed to determine the effect of hospitalisation due to acute illness on the changes in muscle mass and muscle function. The secondary endpoint of the study is to identify health related parameters associated with the development of acute sarcopenia.

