#### **2.2.3. Settings and locations**

The study will be a multicenter study held in different university and tertiary teaching hospitals throughout Europe.

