Nutritional status at admission will be noted via the MNA-SF questionnaire [25], complementary with selected laboratory values. Although aware that malnutrition or starvation during hospitalisation will probably play an important role in development of acute sarcopenia, we chose not to register the actual nutritional intake in hospital with food record charts, because such measurements are very much observer-dependent and hereby very prone to inaccuracy.

The most important advantage of our study is that muscle mass will be measured via ultrasound, which is a relatively new way of sarcopenia screening and assessment [18, 40]. It is much more available than bio-impedance analysis or DEXA, and with less side effects than CT. It can easily be performed on a daily basis in all patients at risk for sarcopenia.

Other strengths of this study are the size of the study population (due to the multicenter setting), the comprehensiveness of assessment and the frequent, regular follow-up measurements.

There are some limitations to the study. Food intake during hospitalization will not be measured. Although nutritional intake is an important factor in retaining muscle mass, it is very difficult to correctly assess caloric and protein intake in acute patients. Also, no good measure for physical activation prior to hospitalisation is included in this research, as making a correct assessment of total exercise time and level through post-hoc recollection is often biased.

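### Section 2.4 compares determinants without accounting for centre: confounding and a modest excess over 5% error for patient-level factors whose frequency differs markedly between centres

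*Combined protocol and SAP*

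**What the plan says.** Section 2.1 sets the design: "A prospective, multicenter, international observational study will be conducted". Section 2.2.3 places it in hospitals that are "held in different university and tertiary teaching hospitals throughout Europe", and section 2.2.1 admits patients from four kinds of ward. The Discussion mentions the multicentre setting only as a source of sample size.

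Section 2.4 is the whole analysis plan: descriptive statistics, a Kolmogorov-Smirnov check of normality, and then "Further statistical analyses will be performed by Chi Square test, Fisher exact, Mann-Whitney U test or Fisher exact test", with P-values of 0.05 or less to be read as significant. No section mentions centre as a stratum, covariate or random effect, and no regression or mixed model is planned.

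Two other provisions bear on the point. Sections 2.3.2 and 2.3.3 let the follow-up measurement depend on ward type and expected stay: 3 days after baseline for short stays, and 7 days (then weekly) for longer ones. Section 2.3.4 collects pedometer data only "in those centers that have access to these devices". The determinants to be tested (section 1.1) are reason of hospitalisation, comorbidities and laboratory data; the Discussion adds nutritional status and frail or sarcopenic status.

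**The concern.** Patients in one hospital share staff, mobilisation practice, case mix and, through ward mix, the interval over which muscle change is measured. Their changes may therefore be correlated. If a determinant is also commoner in some hospitals than in others, an unstratified test attributes part of the difference between hospitals to that determinant.

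Reason of hospitalisation is the clearest candidate. A centre recruiting mainly from orthogeriatrics and one recruiting mainly from internal medicine would differ in reason of admission, and could also differ in length of stay and hence in follow-up interval. The hypothesis in section 1.2, that inflammatory admissions lose more muscle than non-inflammatory ones, is exposed in the same way.

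At stake is the secondary endpoint. Some reported risk factors for acute sarcopenia could be markers of where the patient was treated.

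**Working it through.** **Inputs from the documents.** The only usable figure is the 0.05 threshold in section 2.4; sidedness is not stated, and two-sided is assumed. The documents give no sample size, power, number of centres, centre size or ICC, so there is no figure of the plan's to reproduce.

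**Assumptions.** 10 centres, m = 30 patients each, outcome ICC 0.02 to 0.10, no true effect, and each patient's change compared between two groups.

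**Step 1: clustering of the factor.** For a yes/no factor with centre frequencies p, the factor ICC is Var(p) / [p̄(1 − p̄)]. With 10 centres evenly spaced from 20% to 80%, p̄ = 0.5 and Var(p) = 0.0367, so the factor ICC is 0.0367 / 0.25 = 0.147. For 30% to 70% it is 0.0163 / 0.25 = 0.065. For 40% to 60% it is 0.00407 / 0.25 = 0.016. For a factor constant within a centre it is 1.

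**Step 2: design effect.** DE = 1 + (m − 1) × outcome ICC × factor ICC. Example: 1 + 29 × 0.10 × 0.147 = 1.43.

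**Step 3: actual error of a nominal 5% test.** 2 × [1 − Φ(1.96 / √DE)]. At DE = 1 this returns exactly 5%.

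| Factor across centres | ICC 0.02 | ICC 0.05 | ICC 0.10 |
|---|---|---|---|
| 40% to 60% | DE 1.01, 5.1% | DE 1.02, 5.3% | DE 1.05, 5.5% |
| 30% to 70% | DE 1.04, 5.4% | DE 1.09, 6.1% | DE 1.19, 7.2% |
| 20% to 80% | DE 1.09, 6.0% | DE 1.21, 7.5% | DE 1.43, 10.1% |
| Constant within centre | DE 1.58, 11.9% | DE 2.45, 21.1% | DE 3.90, 32.1% |

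**Step 4: simulated Mann-Whitney tests** (2,000 to 3,000 runs per setting) at ICC 0.02, 0.05 and 0.10:
- 40% to 60%: 5.5%, 5.5%, 5.8%
- 30% to 70%: 6.0%, 6.4%, 7.6%
- 20% to 80%: 6.3%, 7.1%, 9.9%
- constant within centre: 12.7%, 20.9%, 32.2%

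These agree with the formula within simulation error; with 2,000 runs, one standard error is √(0.05 × 0.95 / 2000) = 0.5 percentage points near 5%. At ICC 0 the rates were about 5%.

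**Step 5: sensitivity.** Over 10 to 50 patients per centre and outcome ICC 0.01 to 0.10, the formula gives 5.1% to 10.8% at factor ICC 0.1, 5.3% to 21.2% at factor ICC 0.3, and 6.0% to 42.0% for a centre-constant factor.

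**Step 6: does the remedy work?** For the 20% to 80% factor, the centre-stratified van Elteren test rejected 5.4%, 5.5% and 4.6% of the time at the three ICCs.

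**What these figures leave out.** The centre effects here are unrelated to the factor's frequency. If centres with more of one admission type also systematically use the longer interval, the bias does not average out and the error would be higher. The documents allow no estimate of that.

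**The case against.** The strongest reply is that the alarming percentages belong to a kind of factor this protocol does not name. The listed determinants are all patient-level. Care and mobilisation practice are not recorded anywhere in section 2.3, so they cannot be tested. Pedometer access decides which centres contribute activity data; it is not itself a tested factor. No section says that ward type is fixed by centre, and one hospital may contribute several wards. All of this stands.

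The mechanism also needs care. The outcome is change within a patient, so a constant operator or machine offset cancels. Section 2.3.2 narrows measurement differences further, since "all ultrasonography will be done by an ultrasonographist that is trained to perform the measurements proposed", with probe width, beam frequency and measuring points prescribed. This stands too. What remains as a source of correlated change is care, case mix, unequal follow-up intervals and any proportional or drifting measurement error.

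A reader might infer that every p-value in the study is too small, or that a false-positive rate of 20% to 30% is to be expected. The documents support neither. A determinant spread evenly over centres shows no inflation, and a moderately uneven one shows almost none.

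Finally, section 2.4 has a larger gap: it lists no paired or repeated-measures method, although the primary endpoint is change over time. One model could repair both. But a model with a patient effect alone would still ignore centre, and the centre problem remains if the simple tests are kept. This is a reason to make the two changes together, not to drop this one.

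**Conclusion.** The concern holds in a limited form. The plan's tests ignore centre in a multicentre study, and for patient-level determinants whose frequency differs markedly between centres this confounds the comparison and modestly raises the error: about 6% to 10% for a 20% to 80% spread, and about 5% for 40% to 60%. The 13% to 32% range is a worst case for a factor constant within a centre, and none of the named determinants is shown to be of that kind.

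The absence of any adjustment for centre is a fact of the text. The size rests wholly on assumed centre numbers, centre sizes, ICCs and case-mix spreads; at ICC 0 there is no inflation. The confounding is the more important part for interpretation. The change is worth making because it costs little, not because a large error has been shown.

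**What to change.** In section 2.4:
- Stratify the determinant comparisons by centre, with the van Elteren test in place of Mann-Whitney and the Cochran-Mantel-Haenszel test in place of chi-square or Fisher.
- Alternatively, include centre as a term in any model adopted for change.
- For a factor constant within a centre, use a model with a random centre intercept. The stratified tests have no within-centre contrast and cannot assess such a factor.
- State a rule for pooling very small centres, fixed before the data are examined.

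In section 2.3.1, list centre as a recorded analysis variable. It is not named there, although each patient's hospital will be known.

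The cost is wording and no new measurement. Some precision is lost for factors strongly tied to centre. For a centre-constant factor the loss is large: with the design effects above, standard errors are √1.58 = 1.26, √2.45 = 1.57 and √3.90 = 1.97 times those that the unadjusted analysis implies. Stratifying by centre removes only differences between centres. Unequal follow-up intervals between wards of the same hospital would still need handling in the model for change. The sponsor should also confirm that the named software runs the van Elteren test.
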